#### **6.16.2.4. Time to Admission to ICU from first positive SARS-CoV-2 test**

Time to ICU is defined (in days) as:

$$(First\ study\ day\ when\ ICU\ status\ is\ changed\ to\ "Yes" - Date\ of\ first\ positive\ SARS-CoV-2\ test +1)$$

Only patients who have at baseline or later develop SARS-CoV-2 infection will be included in the analysis. If a patient has been admitted to the hospital or ICU by completion or early discontinuation of the evaluation period, the patient will be censored at the date of their last visit during the evaluation period.

Time to ICU will be evaluated during the study evaluation period only and will be summarized by treatment, and listed for the Prevention and Treatment populations. Cox proportional hazard methodology will be used.

Time to ICU may be presented graphically.

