#### **6.16.1.1. Time to Improvement to Mild Severity Symptoms**

Time to improvement to mild severity symptoms will be is defined (in days) as:

*(Date when participant's symptoms first meet definition of mild severity – Date when participant's symptoms first meet definition of moderate or worse severity + 1)*

Only patients who have at baseline or later develop moderate-or-worse severity COVID-19 will be included in the analysis. If a patient has not experienced improvement to mild symptoms by completion or early discontinuation of the Evaluable Period, the patient will be censored at the date of their last visit during the Evaluation Period.

Time to improvement to mild severity symptoms will be summarized by treatment group and listed for the Prevention populations and the Part 1 Treatment population. In addition, a graphical presentation of the symptom improvement will be provided using a KM plot.

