#### 6.16.1.4. Time to SARS-CoV-2 Clearance

See Section 6.16.1.3 for more details on the definition of viral clearance and date of viral clearance.

Time to SARS-CoV-2 clearance is defined (in days) as:

*(Date of first negative SARS-CoV-2 RT-PCR test – Date of first positive SARS-CoV-2 RT-PCR test + 1)*

Only patients who have at baseline or later develop SARS-CoV-2 infection will be included in the analysis. If a patient has not experienced SARS-CoV-2 clearance by completion or early discontinuation of the evaluation period, the patient will be censored at the date of their last visit during the evaluation period.

Time to SARS-CoV-2 clearance will be evaluated during the study evaluation period only and will be summarized by treatment group, and listed for the Prevention and Treatment populations. Cox proportional hazard methodology will be used.

Time to SARS-CoV-2 clearance will be presented graphically.

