#### 6.16.2.3. Time to Hospitalization from first positive SARS-CoV-2 test

Time to Hospitalization is defined (in days) as:

*(First study day when hospitalized status is changed to “Yes” – Date of first positive SARS-CoV-2 test +1)*

Only patients who have at baseline or later develop SARS-CoV-2 infection will be included in the analysis. If a patient has not been admitted to the hospital or ICU by completion or early discontinuation of the evaluation period, the patient will be censored at the date of their last visit during the evaluation period.

Time to hospitalization will be evaluated during the study evaluation period only and will be summarized by treatment group, and listed for the Prevention and Treatment populations. Cox proportional hazard methodology will be used.

Time to hospitalization may be presented graphically.

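### The censoring rule for time to ICU admission (SAP 6.16.2.4) censors the patients who have the event; read literally, the exploratory Cox analysis has no events

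*SAP*

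**What the plan says.** SAP 6.16.2.4 belongs to the group in 6.16.2, the additional exploratory analyses that the protocol does not define. It sets out five things:

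- **Event and time.** After the words "Time to ICU is defined (in days) as" comes a formula: the first study day on which ICU status becomes Yes, minus the date of the first positive test, plus 1. ICU admission is the event.
- **Analysis set.** "Only patients who have at baseline or later develop SARS-CoV-2 infection will be included in the analysis".
- **Censoring.** "If a patient has been admitted to the hospital or ICU by completion or early discontinuation of the evaluation period, the patient will be censored", with the last visit in the evaluation period as the censoring date.
- **Window.** "Time to ICU will be evaluated during the study evaluation period only".
- **Method.** "Cox proportional hazard methodology will be used".

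The SAP's other rules of this kind run the opposite way. For time to hospitalization (6.16.2.3) the condition is "If a patient has not been admitted to the hospital or ICU by completion or early discontinuation of the evaluation period". For time to viral clearance (6.16.1.4) it is "If a patient has not experienced SARS-CoV-2 clearance by completion or early discontinuation of the evaluation period, the patient will be censored". For time to improvement (6.16.1.1) it is "If a patient has not experienced improvement to mild symptoms by completion or early discontinuation of the Evaluable Period, the patient will be censored".

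**The concern.** A censoring rule should cover the patients who have not had the event. This one covers those who have, and says nothing about the rest. The sentence is complete and grammatical, and it stands in the current body of the SAP, not in the revision history. Nothing elsewhere in the SAP or protocol corrects it.

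What is at stake is whether this analysis can be run from its written rule. If not, someone must decide what was meant, possibly after seeing assignments: the analysis covers the Treatment populations, which include Part 3 (SAP 6.1.1); Part 3 is open label (SAP 5.3.2); and Part 1 data are unblinded to the sponsor at the Part 1 primary analysis (SAP 6.1.5.1).

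**Working it through.** The documents give no event count, power or alpha for this endpoint, so there is no planned figure to reproduce. The check applies each wording to every type of infected patient.

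**Inputs.** The event is ICU status turning to Yes, and only the evaluation period counts (both SAP 6.16.2.4). An ICU admission is taken to be part of a hospital stay. That leaves three patient types: never admitted, hospitalized but never in ICU, and admitted to ICU.

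**Wordings compared.**

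- (a) The sentence as it stands in 6.16.2.4.
- (b) The same sentence with the negative restored, as in 6.16.2.3.
- (c) A condition that refers only to having had no ICU admission.

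| Patient type | (a) As written | (b) Negative restored | (c) ICU only |
|---|---|---|---|
| Never admitted | no rule, no ICU date | censored | censored |
| Hospitalized, never in ICU | censored | no rule, no ICU date | censored |
| Admitted to ICU | censored | event | event |

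**Wording (a).** Let n be the number of patients in an arm admitted to ICU during the evaluation period. All n meet the censoring condition, so the events left are n − n = 0, whatever n is. Later admissions fall outside the window and cannot add any. The Cox partial likelihood is a product over event times; with no events it has no terms and carries no information on the hazard ratio.

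**Wording (b).** ICU admissions become events and never-admitted patients are censored. A patient hospitalized without ICU has no ICU date, so no event, and has been admitted to hospital, so fails the censoring condition. The programmer would have to choose between dropping the patient, censoring at hospital admission and censoring at the last visit. Dropping would exclude patients on a post-randomization outcome that treatment may affect.

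**Wording (c).** Of the three, only this one gives every patient type an outcome.

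**The same check on 6.16.2.3.** There the event is hospitalization. A patient admitted to neither hospital nor ICU is censored, and a hospitalized patient, with or without ICU, has the event. No patient type is left over, so naming the ICU there is redundant but harmless.

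**The case against.** The strongest reply is that this is a typing slip that nobody would program. The event formula is unambiguous and three parallel rules show the intent. Once the negative is restored, ordinary time-to-event practice would censor a patient hospitalized without ICU at the last visit, which is the date the sentence already gives. Most of this stands. A programmer would probably recover the intent, and an analysis with no events is the result of the literal text, not a forecast of what would be reported. What remains is that the written rule is wrong, and the obvious one-word repair still leaves one patient type to an unwritten decision.

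Three stronger conclusions might be inferred, and the documents support none of them.

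- *The ICU comparison is lost.* SAP 6.16.2.5 compares the proportion admitted to ICU by logistic regression in the Prevention and Treatment populations, and 6.12.5 summarizes ICU admission descriptively. Neither uses this rule.
- *The trial's severe-outcome conclusions are affected.* The endpoint is exploratory and outside the testing scheme of SAP 6.5. Hospitalization or death and COVID-19-related deterioration are analysed separately as secondary outcomes (6.10.3.4 and 6.10.3.5).
- *Section 6.16.2.3 has the same fault.* Its rule works as written. Removing the ICU reference corrects no error. Because protocol 8.2.4 records hospitalization and ICU admittance as separate items, the removal could even censor a patient with an ICU entry but no separate hospitalization entry.

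**Conclusion.** The sentence in SAP 6.16.2.4 is wrong as written. It contradicts the section's own event definition and, taken literally, leaves 0 events in every arm. The cause is very probably an omitted negative; that is an inference from the parallel rules, since the SAP nowhere says so. Restoring the negative is necessary but leaves patients hospitalized without ICU admission without a written rule.

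The effect is confined to the timing analysis of one exploratory outcome that the protocol does not define. The primary, key secondary and other secondary analyses do not depend on it. The zero-event result needs only the section's own definitions. The finding that 6.16.2.3 works also rests on ICU admission being part of a hospital stay.

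**What to change.** Replace the censoring sentence in SAP 6.16.2.4 with one that refers only to the ICU, for example: *A patient with no ICU admission by the time they complete, or leave early, the evaluation period is censored at their last visit in that period.* Leave 6.16.2.3 as it is.

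The cost is one SAP sentence. Data collection, sample size, alpha and every other analysis stay the same. The change should be written down before this analysis is run, so that the handling of patients hospitalized without ICU admission is not settled with results in view.

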#### **6.16.2.5. Proportions of Patients Hospitalized, Admitted to the ICU, Requiring Mechanical Ventilation**

The proportion of patients hospitalized, admitted to the ICU, requiring mechanical ventilation (oxygen source = “Intubation/Mechanical Ventilation”) will be evaluated separately using a logistic regression analysis with treatment, facility, and randomization stratification in the model. Missing data will be imputed using the NRI method as described in Section 6.3.3. These endpoints will be evaluated for the Prevention and Treatment populations at Day 57.

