
 Compare the incidence of SARS-CoV-2 infection Compare the frequency of hospitalization or death due to COVID-19 Characterize clinical status for participants. Compare the mortality due to COVID-19 	
 Cumulative incidence of SARS-CoV-2 infection defined as the detection of SARS-CoV-2 by RT-PCR Proportion of participants who are hospitalized or have died due to COVID-19 Proportion (percentage) of participants who experience these events: 
 COVID-19 related hospitalization (defined as ≥ 24 hours of acute care), COVID-19 related emergency room visit, or death Proportion of participants who die due to COVID-19 (according to the investigator)
Exploratory	
[time frame for endpoint evaluation: 8 weeks from randomization]	

 Compare time to improvement to mild severity symptoms in participants who develop moderate or worse severity^a COVID-19 Characterize COVID-19 illness and severity according to NIAID ordinal scale(s) Characterize SARS-CoV-2 viral endpoints in those participants that become RT-PCR positive Characterize emergence of viral resistance to LY3819253 Compare the duration of hospitalization due to COVID-19 	
 Time to improvement to mild severity^a Worst score on NIAID ordinal scale(s) Proportion of participants that achieve SARS-CoV-2 clearance within 1, 2, or 3 weeks of positive RT-PCR Time to SARS-CoV-2 clearance Comparison from the first positive sample to at least the last positive sample Cumulative days of hospitalization in those who are hospitalized due to COVID-19

Abbreviations: COVID-19 = coronavirus disease – 2019; NIAID = National Institute of Allergy and Infectious Diseases; RT-PCR = reverse transcription – polymerase chain reaction; SARS-CoV-2 = severe acute respiratory syndrome coronavirus 2.

^a As defined in [Table 1](#).

Treatment Population Exploratory Objectives and Endpoints Participants positive at baseline for SARS-CoV-2 RT-PCR and negative at baseline for serology Comparison Groups: Placebo vs LY3819253 4200 mg [time frame for endpoint evaluation: 8 weeks from randomization]	
Objectives	Endpoints

 Compare the frequency of hospitalization or death due to COVID-19 	
 Proportion of participants who are hospitalized or have died due to COVID-19

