Part 2 and Part 3 Treatment Exploratory

For Part 3, results from external, non-study SARS-CoV-2 tests will be used to determine eligibility.

Safety, pharmacokinetics, and antidirug antibodies will be characterized in the overall intent to treat population and in the analysis populations.

Treatment Population Exploratory Objectives and Endpoints Participants positive on screening Point of Care Test (Part 2) & positive at baseline for SARS-CoV-2 RT-PCR and negative at baseline for serology	
[time frame for endpoint evaluation: 4 weeks from randomization]	
Objectives	Endpoints

 Evaluate the frequency of hospitalization or death due to COVID-19 Characterize clinical status for participants. 	
 Proportion of participants who are hospitalized or have died due to COVID-19 Proportion (percentage) of participants who experience these events: 
 COVID-19 related hospitalization (defined as ≥ 24 hours of acute care), COVID-19 related emergency room visit, or death

 Characterize COVID-19 illness and severity according to NIAID ordinal scale(s) Evaluate the mortality due to COVID-19 	
 Worst score on a NIAID ordinal scale(s) Proportion of participants who died due to COVID-19

 Characterize SARS-CoV-2 viral endpoints 	
 Proportion of participants that achieve SARS-CoV-2 clearance within 8 or 29 days of baseline Time to SARS-CoV-2 clearance

 Characterize emergence of viral resistance to LY3819253 or LY3832479 Evaluate the duration of hospitalization due to COVID-19 	
 Comparison from baseline to at least the last positive sample Cumulative days of hospitalization in those who are hospitalized due to COVID-19

Abbreviations: COVID-19 = coronavirus disease – 2019; NIAID = National Institute of Allergy and Infectious Diseases; RT-PCR = reverse transcription – polymerase chain reaction; SARS-CoV-2 = severe acute respiratory syndrome coronavirus 2.

^a As defined in [Table 1](#).

4. Study Design

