4.1.2. Evaluation Period

The evaluation period begins when the participant completes screening and is enrolled in the study. Assessments and procedures will be conducted as described in the SoA (Section [1.3](#)).

Participants in Part 1 will be randomized to placebo or LY3819253. The Sponsor will decide when to trigger activation of Part 2. Activation of Part 2 will be communicated to sites.

Participants in Part 2 will be assigned to a cohort as follows:

- Prevention Cohort: Participants who are SARS-CoV-2 negative during screening on the POC test will be randomized to one of three arms: placebo, LY3819253 700 mg, or LY3819253 350 mg + LY3832479 700 mg.
If enrolling to a placebo-controlled trial is challenged by an effective medication becoming available for prevention of COVID-19 and SARS-CoV-2, then the placebo arm may be dropped.

Note: It is possible that some participants have SARS-CoV-2 negative result on the screening point of care test, but could be positive on the baseline SARS-CoV-2 PCR test. The results from the baseline test will not be available until after the participant is randomized. Once positive results are known from the baseline test, these participants will be unblinded and have the option to continue to be followed for safety according to the Prevention Cohort SoA. Unblinded participants will not be included as part of the defined prevention population

The evaluation period for the Prevention Cohort is 8 weeks, with follow-up to Day 169.

- Treatment Cohort: Participants who test SARS-CoV-2 positive during screening with the POC test will be randomized to one of two arms: LY3819253 700 mg, or LY3819253 700 mg + LY3832479 1400 mg.

The evaluation period for the Treatment Cohort is 4 weeks, with follow-up to Day 85.

Participants in Part 3 will be randomized to LY3819253 700 mg or LY3819253 700 mg and LY3832479 1400 mg. The evaluation period for Part 3 is 4 weeks, with follow-up to Day 85. The Sponsor will decide when to trigger activation of Part 3. Activation of Part 3 will be communicated to sites. Part 3 may be activated prior to Part 2.

Part 2 and Part 3 could be activated concurrently. However, Part 3 will not enroll concurrently with Part 2 at the same facility.

Participants will receive one intravenous infusion of study intervention.

The maximum total duration of study participation for each participant of the prevention groups is 24 weeks. See the SOA for prevention groups in Section 1.3.1.

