#### 6.1.1. Analysis Populations

Patient populations are defined in [Table PYAD.6.1](#) along with the analysis they will be used to conduct. The treatment groups and inferential comparisons described in [Table PYAD.6.1](#) will be used unless otherwise specified. Also, unless otherwise specified, for all populations/analysis, patients will be analyzed according to the treatment to which they were assigned.

If enrolling to a placebo-controlled trial is challenged by an effective medication becoming available for prevention of COVID-19 and SARS-CoV-2, then the placebo arm may be dropped in Part 2.

Throughout the document, the term “the Prevention populations” will be used to describe both the Part 1 Prevention and Part 2 Prevention populations. Analyses on the Prevention populations will be conducted on each Prevention population separately. The terms “the Treatment populations” and “the Safety populations” are defined similarly, including those populations from Part 3 of the study.

Table PYAD.6.1. Analysis Populations

Population	Description
Entered	
Definition: All patients who signed informed consent.
 
Purpose: Used for disposition analysis.
 
Treatment Groups: None
 
Inferential Comparisons: None

Enrolled/Intent-to-Treat (ITT)	
Definition: All participants assigned to treatment, regardless of whether they take any doses of study treatment, or if they took the correct treatment. Patients will be analyzed according to the treatment group to which they were assigned.
 
Purpose: Used for disposition, demographic, and safety analyses.
 
Treatment Groups (Short Label):
 
 
Part 1: 4200 mg LY3819253 (4200 LY) and placebo (Pbo)
 
Part 2: 700 mg LY3819253, 350 mg LY3819253 + 700mg LY3832479, and placebo
 
 
Inferential Comparisons: LY versus placebo

Part 1 Prevention	
Definition: All participants in the Enrolled/Intent-to-Treat population in Part 1 who are SARS-CoV-2 RT-PCR negative and serology negative at baseline.
 
Purpose: Used for efficacy and health outcomes analyses.
 
Treatment Groups (Short Label): 4200 mg LY3819253 (4200 LY) and placebo (Pbo)
 
Inferential Comparisons: LY versus placebo

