### ***6.3.3. Non-Responder Imputation (NRI)***

For analysis of other categorical efficacy, missing data will be imputed using a NRI method. Patients will be considered nonresponders for the NRI analysis if they do not meet the categorical efficacy criteria or have missing clinical efficacy data at a time point of interest.

In addition, patients who were not adequately assessed to determine if they meet the clinical requirements for response at the time point of interest are also considered to have failed treatment.

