#### 6.10.3.5. COVID-19-Related Deterioration (Hospitalization, Emergency Room, or Death by Day 57)

Proportion (percentage) of participants who experience deterioration by Day 57 will be analyzed and is defined as:

- COVID-19-related hospitalization (defined as  $\geq 24$  hours of acute care)
- a COVID-19-related emergency room visit, or
- death related to COVID-19

The proportion of patients that experience deterioration by Day 57 will be summarized by treatment group in frequency tables and listed for participants in the Prevention Population.

In addition, the number of patients that experience deterioration by Day 57 will be analyzed using logistic regression to compare each study intervention versus placebo, if there are sufficient data available. Statistical comparisons between each study intervention and placebo will be done using a logistic regression model. The model will include treatment, facility, role within the facility (resident vs staff) and sex as fixed effects. Missing data will be imputed using the NRI method as described in Section 6.3.3.

As an exploratory analysis, this analysis will be repeated on participants in the Treatment populations for events of deterioration up to the end of their respective Evaluation Periods.

#### 6.10.3.6. COVID-19-Related Mortality by Day 57

The proportion of patients that experience death due to COVID-19 by Day 57 will be summarized by treatment in frequency tables and listed for participants in the Prevention Populations.

In addition, the number of patients that experience death due to COVID-19 by Day 57 will be analyzed using logistic regression to compare each study intervention versus placebo, if there are sufficient data available. Statistical comparisons between each study intervention and placebo will be done using a logistic regression model. The model will include treatment, facility, role within the facility (resident vs staff) and sex as fixed effects. Missing data will be imputed using the NRI method as described in Section 6.3.3.

As an exploratory analysis, this analysis will be repeated on participants in the Treatment populations for deaths due to COVID-19 by the end of their respective Evaluation Periods.

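### SAP 6.16.2.5 sets Day 57 for hospitalization, ICU admission and ventilation in every Treatment population, but Part 2 Treatment and Part 3 are evaluated for 4 weeks and have no scheduled daily ventilation record after Day 29

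*SAP*

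**What the plan says.** SAP 6.16.2.5 compares three proportions (hospitalized, admitted to the ICU, mechanically ventilated) by logistic regression, with non-responder imputation (NRI) for missing data. On timing it says: "These endpoints will be evaluated for the Prevention and Treatment populations at Day 57".

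SAP 6.1.1 says that the collective terms for the Treatment and Safety populations "are defined similarly, including those populations from Part 3 of the study". The Day 57 rule therefore covers Part 1 Treatment, Part 2 Treatment and Part 3 Treatment alike.

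The protocol gives these groups different calendars:

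- Part 1 Treatment (Protocol Section 3): "time frame for endpoint evaluation: 8 weeks from randomization".
- Part 2 and Part 3 Treatment (Protocol Section 3): "time frame for endpoint evaluation: 4 weeks from randomization".
- Part 2 Treatment Cohort (Protocol 4.1.2): "The evaluation period for the Treatment Cohort is 4 weeks, with follow-up to Day 85".
- Part 3 (Protocol 4.1.2): "The evaluation period for Part 3 is 4 weeks, with follow-up to Day 85".

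For a closely related outcome, SAP 6.10.3.5 uses a window specific to each group. It repeats the analysis "in the Treatment populations for events of deterioration up to the end of their respective Evaluation Periods".

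The NRI rule in SAP 6.3.3 makes non-responders of patients who fail the efficacy criteria or who "have missing clinical efficacy data at a time point of interest".

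**The concern.** One analysis day has been applied to groups with two different follow-up designs. For Part 2 Treatment and Part 3, Day 57 is not a visit, is not the end of the protocol's evaluation period, and lies beyond the span of daily in-hospital recording. A possible origin is visible in the protocol's amendment history: amendment b moved the treatment cohort's follow-up visit from Day 57 to Day 85.

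Three things are at stake:

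- The ventilation proportion would cover eight weeks although its daily record covers about four.
- The study report could give different counts of hospitalization or ICU admission for the same people, because neighbouring SAP sections use other windows.
- The sentence can be programmed in more than one way. It does not say whether the outcome is status on the day or any event up to it. The NRI rule does not say whether an imputed participant counts as having the event.

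**Working it through.** No sample size, power or alpha figure bears on this point, so there is nothing of that kind to reproduce. The check is date arithmetic and a comparison of sections.

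**1. Does Day 57 fall in a visit window?** Inputs are from Protocol 1.3.1 and 1.3.2.

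- Part 2 Treatment and Part 3: Day 1; Day 8 ± 1 = Days 7–9; Day 29 ± 2 = Days 27–31; Day 85 ± 7 = Days 78–92.
- Day 57 is in none of these. It is 57 − 31 = 26 days after the Day 29 window closes and 78 − 57 = 21 days before the Day 85 window opens.
- In weeks from Day 1: (29 − 1)/7 = 4, (57 − 1)/7 = 8, (85 − 1)/7 = 12. Day 57 is therefore past the 4-week evaluation period but inside the 12-week follow-up.
- Part 1 has a visit at Day 57 ± 2 = Days 55–59, so Part 1 Treatment is unaffected.

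**2. What data exist up to Day 57 in Part 2 Treatment and Part 3?**

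- *Hospitalization and ICU admission.* Protocol 8.2.4 has the dates of these events entered in the CRF, and the schedule in 1.3.2 marks hospitalization events at Days 1, 8, 29, early termination and 85. A participant seen at Day 85 can be classified through Day 57.
- *Mechanical ventilation.* This comes from the record of in-hospital status and procedures. The visit-type table in Protocol 4.1.2 schedules that record daily for Days 2–29. Days 30–57 are 57 − 29 = 28 of the 57 − 1 = 56 days after Day 1, which is 28/56 = 50%. For that half, ventilation depends on retrieving hospital records at early termination or Day 85. As extracted, the schedule row for this item appears to have no Day 85 mark, but its columns are not cleanly aligned, so nothing here rests on it.

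**3. Does Day 57 agree with the SAP's other windows for these groups?**

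- 6.10.3.5 and 6.10.3.6 (deterioration, COVID-19 death): end of each population's own Evaluation Period.
- 6.16.1.3 (viral clearance): 8 and 29 days for Part 2 Treatment and Part 3, against 1, 2 or 3 weeks elsewhere.
- 6.16.2.3 and 6.16.2.4 (time to hospitalization, time to ICU): restricted to the evaluation period.

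The length of that period is itself unsettled. The protocol says 4 weeks, ending at Day 29. SAP Table PYAD.6.2 ends it at the first follow-up visit if the participant has not discontinued earlier, and in these groups that visit is Day 85. Day 57 matches neither:

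- With the protocol's period, an admission on Day 40 counts in 6.16.2.5 (40 ≤ 57) but not in 6.16.2.3 (40 > 29).
- With the SAP table's period, an admission on Day 70 counts in 6.16.2.3 if the follow-up visit comes later, but not in 6.16.2.5 (70 > 57).

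**4. Which way does NRI impute?** SAP 6.3.3 is written for response. Its second paragraph treats inadequately assessed patients as treatment failures, which for these outcomes would suggest imputing the event. Its first paragraph groups missing patients with those who do not meet the criterion. If the criterion is taken to be hospitalization, that would suggest imputing no event. The section does not choose.

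**5. How many people?** Part 3 enrols 30 to about 500. For Part 2, 2000 − 1700 = 300 is a rough figure for the Treatment Cohort. Protocol 9.2 treats the 1700 as the Prevention Cohort, but the synopsis describes them as RT-PCR and serology negative, so the remainder may include others. The Treatment populations are the RT-PCR-positive, serology-negative subsets (Protocol 9.3). The documents do not give that fraction, so 500 and 300 are enrolment figures and the numbers analysed will be smaller.

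**The case against.** A reader might infer that, with no Day 57 visit, NRI would class every Part 2 Treatment and Part 3 participant as missing and leave the comparison without information. The documents do not support that. SAP 6.3.3 does not equate the lack of a visit with missing data. Hospitalization and ICU events carry dates and are collected again at Day 85. SAP 6.1.3 reads by-day endpoints cumulatively and, outside the infection endpoints, allows results from visits outside the window. SAP 6.12.5 lists the same outcomes as events observed at any time in the evaluation period. Those missing would be participants lost before Day 57 or without later ascertainment, not everyone.

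Four further points favour the sponsor.

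- The 4-week time frame heads the protocol-defined endpoints, and 6.16.2.5 is an analysis added by the SAP, so no protocol endpoint is breached. This stands.
- SAP 6.12.5 already gives evaluation-period proportions descriptively. This stands too, and lowers the cost of leaving 6.16.2.5 alone.
- Protocol 8.2.5 sets no last day for recording procedures, and 4.1.2 provides for retrieving hospital records. This stands in part: ventilation in Days 30–57 is not shown to be absent, but no scheduled daily record covers it.
- Keeping Day 57 and deriving events from dates collected through Day 85 would be coherent for hospitalization and ICU admission. That is true, but it does not supply ventilation or align the window with the sibling analyses.

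**Conclusion.** The time point in SAP 6.16.2.5 is wrong as written for Part 2 Treatment and Part 3 and right for the Prevention and Part 1 Treatment populations. The substantive weakness is ventilation in Days 30–57, half of the post-Day 1 window. For hospitalization and ICU admission the problem is inconsistent windows, not absent data. The wording of the time point and the direction of imputation also need settling.

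Severity is low. The three analyses are exploratory, Part 3 is not powered for inference between its arms, and no primary, key secondary or protocol-defined endpoint is touched.

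The conclusion assumes that the Days 2–29 entry in the Protocol 4.1.2 visit-type table governs daily collection, and that Day 85 contacts capture event dates as Protocol 8.2.4 describes.

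**What to change.** Replace the timing sentence in SAP 6.16.2.5 with text to this effect: each outcome is the occurrence of at least one dated event after randomization, by Day 57 in the Prevention populations and the Part 1 Treatment population, and by Day 29 in the Part 2 Treatment and Part 3 Treatment populations.

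Name Day 29 outright. Referring to the end of the Evaluation Period would not be enough, because SAP Table PYAD.6.2 carries that period to the first follow-up visit, Day 85 in these groups.

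Add one sentence stating whether a participant imputed under NRI counts as having the event.

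The cost is two sentences in the SAP, with no new visits, data or protocol amendment. Part 3 is open label, so the change is best made before its outcomes are tabulated by arm.
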